#### A. Research Procedures

Procedure (in order of occurrence)	When	Where	By Whom
Recruitment of Participants Cross-sectional phase and interventional phase	May 2022-June 2024	various HIV treatment centers in the NJ region and/or HIV support groups	[name] [name] [name]  [name]
Screening for Eligibility Cross-sectional phase and interventional phase	May 2022–June 2024	By phone or HIPAA compliant ZOOM meeting	[name]  [name]
Consenting Cross-sectional phase and interventional phase	May 2022–June 2024	Rutgers study site (in Newark or Voorhees) or Wm Way Center in Philadelphia	[name]  [name]
Baseline Testing (Week 0) Cross-sectional phase and interventional phase	May 2022–June 2024	Rutgers study site (in Newark or Voorhees) or Wm Way Center in Philadelphia for in-person tests and questionnaires Physical activity monitoring done at home	[name] [name] [name]  [name]
Group assignment and instruction in interventions for TENS and MM groups Interventional phase only	May 2022–June 2024	Rutgers study site (in Newark or Voorhees) or Wm Way Center in Philadelphia	[name] [name]  [name]
Home-based Interventions and daily	May 2022–July 2024	Participant's home	Participant

question re: adherence via text message (6 weeks) Interventional phase only			
Post-intervention Testing (Week 7) Interventional phase only	May 2022–July 2024	Rutgers study site (in Newark or Voorhees) or Wm. Way Center in Philadelphia for in-person tests and questionnaires Physical activity monitoring done at home	[name] [name] [name]  [name]
Follow up Questionnaire (Week 15) Interventional Phase only for those who were in TENS or MM groups and enrolled after IRB approval to add follow up questionnaire.	April 2024 – Sept. 2024	Participant's home or location of choice via Email/RedCap	[name]

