**Procedures to monitor subjects for safety and minimize risk of harm during testing:** Study staff will follow CDC and Rutgers COVID precautions that are in place at the time (such as wearing a face mask and a face shield) throughout the testing session. Study staff will wash their hands before and after a testing session and sanitize their hands frequently throughout a testing session. All equipment including pens or iPads used for questionnaires will be disinfected both prior to and immediately following a testing session for a given participant. Participants will be scheduled one at a time with no overlap. If more than one participant is scheduled on the same day, there will be a full hour gap between participants to allow time for disinfection of all testing equipment. Participants' appointments will be postponed if they are experiencing symptoms of COVID-19 or are febrile or had a high risk exposure to a COVID infected individual during the week prior to their testing appointment. This will be determined by the PI or study staff calling the participant the day prior to or the morning of their appointment. Prior to testing procedures, participants' resting heart rate, blood pressure, respiratory rate and temperature will be taken. If vital signs values or temperature are outside of acceptable ranges, testing will not proceed on that date. All participants will be required to follow COVID precautions that are in place at the time of testing throughout the testing session. Currently, this includes participants wearing masks throughout the session, sanitizing their hands with hand sanitizer prior to the start of testing and prior to leaving the testing session, and maintaining social distance of at least 6' between study team personnel and participants will be maintained except for when testing procedures require closer proximity. All participants will be guided by and supervised by a study team member throughout all testing procedures. During the balance tests that are included the Short Physical Performance Battery, the PI or his designated study team member will stand adjacent to the participant and provide guarding in case the participants experience a loss of balance. The other test that will require proximity of less than 6' is pain pressure threshold testing. After each test, participants will be asked if they would like to sit and rest before continuing on to the next test. If participants appear to be in any distress or become lightheaded during testing, they will be given the option of lying down on a treatment table or sitting in a chair, and their vital signs will be reassessed.

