
**Procedures to monitor subjects for safety and minimize risk of harm during the period of home-based interventions:** Participants in the interventional phase will be notified on baseline testing day that they should contact the PI if any problems arise during the 6 week at-home

intervention period. Participants in the TENS will be educated on how to inspect their skin after removing electrodes following a TENS treatment. Because DSP typically causes impaired sensation in the distal extremities TENS electrodes will not be placed on the feet. Rather, the locations will be more proximal at designated points on the lower extremities that have been assessed (on the day of baseline testing) by study personnel to have protective sensation as assessed with a 5.07 gauge (10 gram) Semmes-Weinstein monofilament. Participants in the TENS group who do not have protective sensation over the TENS sites in the legs will NOT be provided with TENS treatment. In addition, participants will be contacted once a week by text message meeting and will be asked if they are experiencing any problems or difficulties with the home-based interventions.

**Randomization:** The cross-sectional phase does not require randomization. For the interventional phase, participants with DSP will be randomly assigned to either the TENS group or the MM group or the standard care group (SC) using a web-based random number generator (<https://www.randomizer.org/>) that will link a group code (TENS, MM, or SC) to a participant's study ID number. Once a participant has been randomized to a group, the matching of the participant's ID number and assigned group will be delivered a study team member in a sealed opaque envelope.

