Digital Algometer	The blunt tip of the algometer is placed along the dorsal web-space (between 1 st and 2 nd toes) or the proximal	Vaughan, B., McLaughlin, P., & Gosling, C. (2007). Validity of an electronic pressure algometer. International Journal of Osteopathic Medicine , 10(1), 24-28.

	lateral tibia just below the lateral tibial plateau. Pressure is slowly increased until subject reports it is painful, after which the pressure is removed. The value (threshold) is recorded.	Vaughan, B., McLaughlin, P., & Gosling, C. (2007). Validity of an electronic pressure algometer. International Journal of Osteopathic Medicine , 10(1), 24-28.
Brief Pain Inventory	Questionnaire, subscale scores for Pain Intensity and Pain Interference calculated based on responses to questions.	Cleeland, C. S., & Ryan, K. M. (1994). Pain assessment: Global use of the Brief Pain Inventory. Annals Academy of Medicine, Singapore , 23(2):129-138. Keller, S., Bann, C. M., Dodd, S. L., Schein, J., Mendoza, T. R., & Cleeland, C. S. (2004). Validity of the brief pain inventory for use in documenting the outcomes of patients with noncancer pain. The Clinical Journal of Pain , 20(5), 309-318.
Medical Outcomes Study HIV Health Survey (MOS-HIV)	Questionnaire, subscale scores for Physical Quality of Life and Mental Quality of Life are calculated based on responses to questions.	Wu AW, Revicki DA, Jacobson D, Malitz FE. (1997). Evidence for reliability, validity and usefulness of the Medical Outcomes Study HIV Health Survey (MOS-HIV). Qual Life Res , 6(6):481-493.
Hospital Anxiety and Depression Scale (HADS)	Questionnaire, subscale scores for depression or anxiety calculated based on responses to questions.	Bjelland, I., Dahl, A. A., Haug, T. T., & Neckelmann, D. (2002). The validity of the Hospital Anxiety and Depression Scale: an updated literature review. Journal of Psychosomatic Research , 52(2), 69-77. Stern, A. F. (2014). The hospital anxiety and depression scale. Occupational Medicine , 64(5), 393-394.

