**E. Minimizing Risks of Harm**

**Procedures to assure confidentiality of data:**

All data will ultimately be stored in a password protected folder on the university servers and accessible only to appropriate project team members. Data will be linked only to participant study ID#,s, i.e. key codes. The de-identified data file will be shared with [name] (co-investigator and statistician) and other co-investigators as needed for purposes of analysis. A separate secure spreadsheet that links participant ID#s to their names will be kept on a separate password protected folder on a university server available only to [name] (PI) and [name] (co-investigator) and will be accessed only if the code needs to be broken in order to contact a participant based on any measurements or questionnaire responses that suggest need for a referral for medical attention or counseling. Signed consent forms will be scanned into a separate secure password protected folder on the university servers and accessible only to appropriate project team members, after which paper copies will be shredded. [name] (PI) is responsible for assuring security of all de-identified data, the spreadsheet that links participant names to

participant ID#s, and signed consent forms. Any co-investigators and study staff involved with data collection ([name], [name], [name]) will be trained by PI ([name]) in all security protocols.

Data will be entered into the RedCap platform and RedCap via survey links that are created for this study, and will later transferred to in a password protected folder on the university servers and accessible only to appropriate project team members.

ZENO walkway data will be stored and processed on a password protected laptop dedicated to the ZENO walkway. The laptop with ZENO walkway data will be continuously within the line of sight of [name] or [name] during data collection and securely stored during transport between data collection locations. ZENO walkway data will be transferred from the dedicated laptop to a secure password protected folder on the university servers. After processing ZENO walkway data with PKMAS gait analysis software, the raw and aggregate ZENO walkway data will be uploaded into the RedCap project.

Mid-thigh pull test data will be uploaded into the RedCap project.

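### Nothing in the plan keeps the Week 7 tester unaware of the arm (Aim 2); as a separate gap, nothing hides neuropathy status from the Week 0 tester (Aim 1)

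*Combined protocol and SAP*

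**What the plan says.** The Randomization paragraph of Section 1.3 A links a group code to each study ID by a web-based generator. It then says that the matching of ID and "assigned group will be delivered a study team member in a sealed opaque envelope". It does not identify the recipient, say when the envelope is opened, or restrict what that person may do afterwards.

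The procedures table in Section 1.3 A has one row for "Group assignment and instruction in interventions for TENS and MM groups" and a later row for Week 7 testing. On conduct of testing it says "All participants will be guided by and supervised by a study team member throughout all testing procedures", and for the SPPB balance tests that "the PI or his designated study team member will stand adjacent to the participant and provide guarding". During the home period, participants are told that they "should contact the PI if any problems arise during the 6 week at-home" intervention. Section 6.3 A repeats that route by weekly text message and has the PI review Week 7 data within 24 hours of collection.

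Section 1.3 B repeats all Week 0 measurements at Week 7 and adds a satisfaction questionnaire, which Section 1.9 says is completed on site. Among the Study Instruments in Section 1.9, the algometer entry reads "Pressure is slowly increased until subject reports it is painful, after which the pressure is removed". Masking appears in the available text only as face masks for COVID-19.

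**The concern.** Participants cannot be masked to TENS, meditation or standard care. For the measurements that a staff member administers, the remaining protection is a tester who does not know the arm, and the plan does not provide for one. The expected direction is also written down: Section 1.1 B predicts benefit on every outcome in both active arms, and Section 4.7 F calls the probability of benefit high. A tester who knows the arm may, without intending to, raise the algometer pressure more slowly, start or stop a stopwatch differently, or urge a harder pull.

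At stake are the effect sizes that Sections 1.4 and 1.5 name as a product of the pilot. A future trial planned on estimates shifted in the hoped-for direction would be too small.

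**Working it through.** 1. **The plan's own figure.** The only calculated figure is enrolment (Section 1.5): 72 / 0.90 = 80 and, for the interventional phase, 36 / 0.90 = 40. Both reproduce. Neither bears on this point. No alpha, power, effect size or SD is stated.

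2. **How a Week 7 tester could know the arm.** The text leaves four routes open. The tester may have opened the envelope or instructed the participant (1.3 A). The tester may have seen the daily adherence replies, which only the TENS and meditation groups send (1.3 B). The tester may be the PI, who receives problem reports and may guard the SPPB (1.3 A, 6.3 A). Or the arm may come out through the on-site satisfaction questionnaire, because no order relative to the physical tests is given and Section 4.1 C lets staff read questions aloud.

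3. **Which outcomes are exposed (Section 1.9).**
   - Algometer: the tester raises the pressure by hand, at no stated rate.
   - SPPB: timed by stopwatch.
   - Mid-thigh pull: a force-gauge reading, but of a maximal voluntary pull, so coaching matters.
   - 6-Minute Walk: self-selected pace, laps counted, last part-lap measured with a wheel. Only cueing could act. Walkway gait data come from laps of the same walk and share that exposure.
   - Wrist actigraphy and self-completed questionnaires depend little on the tester.

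4. **Baseline does not cancel it.** The procedures table is in order of occurrence and puts Week 0 testing before assignment. Week 0 values therefore cannot carry an arm-dependent tester effect, and a Week 7 effect goes straight into the change from baseline.

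5. **Effect on the estimate.** With true difference d and tester-induced shift b, both in SD units, the expected estimate is d + b. Sample size does not enter. The unadjusted standard error does shrink with n: sqrt(2/12) = 0.41 SD at 12 per arm and sqrt(2/36) = 0.24 SD at 36 per group.

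6. **Illustration on assumed values.** The documents give no value for b. Assume no true effect, a two-sample t-test and two-sided alpha 0.05; this simplifies the planned three-group repeated-measures analysis. The noncentrality is b × sqrt(n/2), with sqrt(12/2) = 2.449 and sqrt(36/2) = 4.243.

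| Assumed b (SD) | Noncentrality, n = 12 | False-positive rate | Noncentrality, n = 36 | False-positive rate |
|---|---|---|---|---|
| 0 | 0 | 5% | 0 | 5% |
| 0.2 | 0.49 | 7.6% | 0.85 | 13.3% |
| 0.3 | 0.73 | 10.8% | 1.27 | 24.1% |
| 0.5 | 1.22 | 21.6% | 2.12 | 55.3% |

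   The 12-per-arm columns concern arm knowledge in Aim 2. The 36-per-group columns concern knowledge of neuropathy status in Aim 1.

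7. **Aim 1, taken separately.** Aim 1 uses Week 0 data only (Section 1.9, Timing and Frequency). Neuropathy status is set beforehand, at the phone or video screen by the PI or study staff (Section 4.1 C). Nothing conceals it from the Week 0 tester. The planned session lengths, 45 minutes without neuropathy and 1.5 hours with it, could also give it away. The confounder adjustment in Section 6.1 addresses differences between participants and would not remove a tester effect.

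8. **Staffing.** The procedures table has three name positions for assignment and instruction and four for Week 7 testing. If each position were a different person, at least 4 − 3 = 1 tester would be outside assignment. With names removed, the overlap cannot be seen.

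**The case against.** The strongest reply is that this is a small feasibility pilot with unmasked participants, so separating roles can only partly reduce bias. That stands. Self-reported outcomes stay unmasked whatever is done, and participants may reveal their group.

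The exposure is also uneven. No encouragement is described for the 6-Minute Walk. The mid-thigh pull is scored by a gauge. The algometer endpoint is the participant's own report of pain, so a masked tester protects only the way the pressure is applied. Actigraphy and the instrumented walkway are already fairly robust. This narrows the point to the pressure ramp, SPPB timing and coaching of the pull, with cueing a lesser matter for the walk. It does not answer the point, because these tests are repeated at Week 7 with no safeguard.

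The roles may also be separated in practice. Names are removed, and Sections 2.1 (staff) and 2.4 (sites) are not in the available text. That limits what can be said about who does what. It does not alter Section 1.3 A, where the rule belongs and is absent.

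A reader might infer that the team already has enough people, so that masking needs no extra staff. The documents do not show this. Name positions are not reliably one person each: in Section 4.4 A they stand in a list of sites. Testing is spread over Newark, Voorhees and Philadelphia, and Section 2.2 has a different trainer for the walkway and mid-thigh pull. One free tester might not cover every session.

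**Conclusion.** The concern holds for Aim 2. As written, the plan lets a person who knows the arm run the Week 7 tests, and the algometer, SPPB and mid-thigh pull are the outcomes most open to it. The size of any bias cannot be derived from the documents. What can be said is that it would enter the pilot's effect sizes in full at any sample size. The error rates in the table rest wholly on the assumed shifts and the simplified test.

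Two stronger readings are tempting and should not be drawn. One is that knowledge of the arm biases both aims. It cannot bias Aim 1, whose data are collected before any arm is assigned; Aim 1 has its own gap, about neuropathy status. The other is that observer bias would make up some stated share of the treatment effect. The documents give neither the bias nor the effect, so any such percentage would be a ratio of two assumptions.

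The change is worth making because it is cheap. It reduces the risk but does not remove it.

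**What to change.** Add a paragraph to Section 1.3 A with these elements.

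1. State who opens the envelope and instructs the participant. Where staffing allows, have a different listed team member run the Week 7 algometer, SPPB, mid-thigh pull and 6-Minute Walk with its gait recording. That person should not have seen the participant's adherence or problem texts. The PI should not test participants whose arm the PI knows; the existing provision for a designee at the balance tests already permits this.
2. Use a fixed script for these tests, and run them before the Week 7 questionnaires, including the satisfaction questionnaire.
3. Ask participants not to name their group. Record any unmasking and, for each session, whether the tester knew the arm.
4. Have the allocation list held by someone other than the analysing statistician, or give the analyst coded groups. The statistician receives the ID-linked data file (Section 6.2), so holding the list as well would unmask the analysis.

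For Aim 1, as a separate sentence: at Week 0, run the physical tests from the same script before the questionnaires given only to those with neuropathy and, where possible, by someone who did not do the screening.

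The cost is one protocol paragraph, a short script, one extra recorded item and less freedom over who tests on a given day. Where separation is not feasible at a site, the script, the test order and the record of tester knowledge still help.

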## B. Data Points

Data elements include an array of non-invasive physical performance tests, physical activity monitoring, pain pressure threshold testing, and questionnaires. See Section 1.6 B. for detail on dependent variables/outcome measures.

The data elements will be collected at baseline (Week 0) for all participants.

At Week 0, all participants complete a demographic and health questionnaire and a physical activity questionnaire, the Brief Pain Inventory, and will undergo testing related to gait, walking endurance, physical performance, and pain-pressure threshold. They will receive a physical activity monitor that they will be asked to wear for 5 days and then ship back to the PI in a pre-paid shipping box.

Those with DSP-related pain will also complete questionnaires for pain, quality of life, depression and anxiety, catastrophizing behavior, and resilience at Week 0.

Those participants with DSP-related pain will be randomized to continue on to the interventional phase. Throughout the 6-week intervention period, participants in the TENS and MM groups will receive a daily text message in the morning that will ask them if they completed the home-based treatment on the day prior, and a weekly text message to ask if any problems have emerged; participants in the standard care group will receive a weekly text message to ask if any problems have emerged. All participants in the interventional phase will return for follow up testing after 6 weeks of intervention (Week 7), at which time all measurements taken at Week 0 will be repeated. In addition, participants will complete a satisfaction questionnaire at Week 7. They will once again receive a physical activity monitor that they will be asked to wear for 5 days and then ship back to the PI in a pre-paid shipping box. In addition, those who were randomized to the TENS or MM groups starting in March 2024 will complete a short follow up questionnaire at Week 15.

## C. Study Duration

72-80 participants will be seen one time for testing, followed by 5 days of physical activity monitoring for the cross-sectional phase.

The 36-40 participants without DSP will be engage for approximately one week (baseline testing followed by 5 days of activity monitoring).

The 36-40 participants with DSP-related pain will continue with the interventional phase for 6 weeks (home-based treatment or usual care/control) then return for post-intervention testing at week 7, followed by 5 days of activity monitoring. At week 15, those who were randomized to the

TENS or MM groups will receive a short follow-up questionnaire via email/RedCap. Overall, those with DSP (interventional phase) will be participating for approximately 8 weeks if in the Usual Care Group, or 15 weeks if in the TENS or MM groups (to account for the follow up questionnaire).

The overall duration of the study is expected to be 12 months. Participants will be enrolled on a rolling basis as determined by their availability for test dates and times.

#### D. Endpoints

Study end point for those participants without DSP (cross-sectional phase only) will be 5 days after the date of a participant's on-site baseline testing. (Following on-site baseline testing, they will continue to wear an activity monitor for 5 days). Study end point for those participants with DSP and randomized to the Usual Care group will be approximately 8 weeks from the date of on-site baseline testing, allowing for 5 days of activity monitoring after on-site baseline testing, 6 weeks of home based intervention, on-site post-intervention testing, and 5 days of activity monitoring after the on-site post-intervention testing. Study end point for those participants with DSP and randomized to the TENS or MM groups will be approximately 15 weeks from the date of on-site baseline testing, allowing for 5 days of activity monitoring after on-site baseline testing, 6 weeks of home based intervention, on-site post-intervention testing, 5 days of activity monitoring after the on-site post-intervention testing, and finally a follow up questionnaire at week 15. All test procedures are expected to be safe. However, any participants who report increased physical or emotional distress during testing will be invited to rest so that study staff can reassess their vital signs and determine if the participant can continue if they choose to do so. Testing procedures will cease if a participant falls or sustains any form of injury during the testing.

Although the interventions (TENS, mindfulness meditation) pose negligible risk, if a participant experiences a serious adverse event, that participant will be withdrawn from the study. Any adverse events will be reported to the IRB. Furthermore, participants can elect to withdraw themselves from the study at any time.

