#### 1.5 Sample Size Justification

A sample of 80 participants will be enrolled in the cross sectional phase and 40 participants (those with DSP) will continue on to the interventional phase.

The target sample size of 72 (36 with DSP and 36 without DSP) for the cross sectional phase is adequate to explore of between group differences in gait, physical performance, physical activity, and pain pressure threshold variables. For the interventional phase, 36 participants (12 participants in each of the 3 groups) is adequate to demonstrate feasibility and determine effect sizes that can inform a future randomized controlled trial. The expected accrual rate is 90% (drop-out rate of <10%); thus, the number enrolled will be 80.

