## 6.0 Data Management Plan

### 6.1 Data Analysis

Cross-sectional phase: We will test for baseline differences between those with painful DSP and those without painful DSP for the set of variables using independent t-tests (or Mann-Whitney tests if distributions are non-normal). Differences between those with and without DSP on potential demographic or clinical confounders will be adjusted for statistically.

Interventional phase: Assuming normality of the outcome variables of interest, between group repeated measures analysis of variance will be used to evaluate differences within and between groups for each outcome separately. In the case of non-normal outcome variable distribution, we will consider transforming the measure to normalize. If normalization is not warranted, then within group changes will be tested using a Friedman's test and between group differences will be compared descriptively. Data will be analyzed using both per-protocol and intention-to-treat analyses in the case of dropouts.

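### Withdrawing a participant from the study after any serious adverse event removes the only post-baseline outcome visit if the event comes before Week 7, leaving no observed outcome for the intention-to-treat analysis

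*Combined protocol and SAP*

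**What the plan says.** Section 1.3 D (Endpoints) states that "if a participant experiences a serious adverse event, that participant will be withdrawn from the study". The sentence opens by noting that TENS and meditation carry negligible risk, but the rule itself has no condition on relatedness, arm or timing. The participant's own right to leave at any time is given separately, so this is an exit imposed by the protocol.

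Section 1.3 B brings every interventional-phase participant back at Week 7 to repeat all Week 0 measurements. The table in section 1.6 B shows no other post-baseline assessment of the clinical and functional outcomes. Weeks 1 to 6 record adherence only. Week 15 covers continued use of the interventions, in two arms only: "those who were randomized to the TENS or MM groups starting in March 2024 will complete a short follow up questionnaire at Week 15".

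For the analysis, section 6.1 says that "between group repeated measures analysis of variance will be used to evaluate differences within and between groups for each outcome separately" and that "Data will be analyzed using both per-protocol and intention-to-treat analyses in the case of dropouts". It defines neither analysis set and gives no method for a missing Week 7 value.

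Section 6.3 A has the investigator review each participant's Week 7 data within a day for signs of harm. On numbers, section 1.5 says that "36 participants (12 participants in each of the 3 groups) is adequate to demonstrate feasibility and determine effect sizes".

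**The concern.** An intention-to-treat analysis is most useful when outcomes are sought from everyone randomised, whether or not they continue the intervention. Here the protocol stops seeking the outcome after a defined post-randomisation event. That makes the missing data avoidable, and possibly informative if a serious event is related to pain, function or quality of life. As worded, the rule also covers the standard care arm, where there is no study intervention to stop.

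At stake are the effect sizes that this pilot is meant to pass on to a future trial. In arms of about 12, one or two lost participants can shift an estimate. A participant withdrawn after a serious event also misses the scheduled Week 7 review for harm.

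**Working it through.** **1. The plan's own figures.** Section 1.5 says "A sample of 80 participants will be enrolled in the cross sectional phase and 40 participants (those with DSP) will continue" and "The expected accrual rate is 90% (drop-out rate of <10%); thus, the number enrolled will be 80". Enrolled = completers / (1 − drop-out):
- cross-sectional phase: 72 / 0.90 = 80
- interventional phase: 36 / 0.90 = 40

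Both are reproduced. The interventional phase can lose 40 − 36 = 4 participants from all causes before it falls below target.

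**2. What is lost, by timing of the event.**
- *Before the Week 7 visit:* all post-baseline clinical and functional outcomes and the Week 7 harm review. Repeated measures ANOVA in its standard form needs both Week 0 and Week 7, so the participant drops out of the model.
- *After the Week 7 visit:* at most the second 5 days of activity monitoring and, in the TENS and meditation arms, the Week 15 questionnaire.

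The documents do not say in so many words that Week 7 testing is cancelled. That follows from withdrawal from the study, and no section restores the visit.

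**3. How many.** The documents give no serious-event rate, so the rate p before Week 7 is an assumption. Expected losses = 40p; chance of at least one = 1 − (1 − p)^40.

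| Assumed p | Expected losses of 40 | Chance of at least one |
|---|---|---|
| 1% | 0.4 | 33% |
| 2% | 0.8 | 55% |
| 5% | 2.0 | 87% |

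**4. Effect on numbers.** One participant is 1/12 = 8% of a target-size arm. One or two losses use 1/4 to 2/4 of the allowance of four. If other drop-out had already used the allowance, one or two more would leave 40 − 4 − 1 = 35 or 40 − 4 − 2 = 34 completers against the target of 36.

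**5. Possible bias (illustration).** Assume 13 randomised to an arm (40/3 is about 13.3), with k withdrawn who would each have scored d SD worse than that arm's completers. The completer mean is then too favourable by k × d / 13. With d = 1:
- k = 1: 1/13 = 0.08 SD
- k = 2: 2/13 = 0.15 SD

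For scale, the standard error of a difference between two arms of 13 is √(2/13) = 0.39 SD. The bias is modest beside the sampling error, but it depends on a value of d that nothing in the documents establishes.

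**The case against.** **The sections do not contradict each other.** A reader might infer that 1.3 D and 6.1 flatly conflict. They do not: 6.1 expects drop-outs, and a withdrawal after a serious event is one kind of drop-out. This stands. The problem is a tension, in which one section creates missing outcomes and the other has no stated way to handle them. The missing-data gap affects every drop-out; what is particular here is that the protocol causes the loss.

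**The rule may be meant only for harm from the interventions.** The opening clause allows that reading. The rule does not say so, however, and the ambiguity itself needs settling.

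**Nothing shows that these participants did worst.** That is a tempting inference, but a serious event may have no bearing on foot pain, gait or quality of life. This stands: informative loss is possible, not shown.

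**Safety oversight does not end.** A reader might infer that it does. Yet reporting of adverse events to the IRB (1.3 D, 6.3 A), the investigator's record of problems (6.3 A) and referral for illness or injury caused by participation (2.3) are not cancelled. Only the scheduled Week 7 review is lost.

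**The consequence is small.** The study is described as minimal risk and is a pilot without a powered test. Even at 5%, the expected two losses fit within the allowance of four, which is not reserved for other causes. This limits the importance of the point but does not justify discarding data that could be collected.

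**Week 7 testing after a serious event is partly a clinical decision.** It includes a 6-minute walk and a maximum-effort pull. This stands, and the choice of assessments belongs with the investigator.

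**Conclusion.** The point holds as a minor, inexpensive improvement. As written, a serious adverse event before Week 7 ends participation and with it the only post-baseline measurement of the effect outcomes, so the participant cannot contribute an observed outcome to the intention-to-treat analysis. Under an assumed 1% to 5% rate before Week 7, 0.4 to 2 of 40 participants are expected to be affected. The actual number could be zero.

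This rests on three things: reading withdrawal from the study as ending Week 7 testing, the standard form of repeated measures ANOVA, and an event rate that the documents do not supply. They do not support saying that the two sections are irreconcilable, that the loss is known to be informative, or that all safety follow-up stops. When the intervention itself should stop is a clinical matter and is not judged here.

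**What to change.** Reconcile sections 1.3 B, 1.3 D, 6.1 and 6.3 A:

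- In 1.3 D, separate stopping the intervention (a clinical decision, not addressed here) from leaving the study, and say whether the rule is meant to cover events of any cause and all three arms.
- State that a randomised participant who has a serious adverse event and agrees remains in follow-up for outcome data. Week 7 would then consist of whatever assessments the investigator judges suitable, at least the questionnaires, completed remotely if needed.
- In 6.1, state that such a participant is analysed in the assigned arm, and how a Week 7 value that is still missing enters the intention-to-treat analysis.
- Have the Week 7 review in 6.3 A cover whatever data are obtained.

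The cost is a few sentences and minor extra work. The data-collection table lists the outcome questionnaires as completed on-site, so remote completion needs a provision, but they are already web-based and the Week 15 questionnaire is already completed off-site. Physical tests may still be missing for some participants. The protocol version is dated March 2024 and its timetable ends recruitment in June 2024, so the change can help only participants who have not yet reached Week 7. For anyone already withdrawn under the rule, the report should give the number by arm.
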